**Optimizing the Effectiveness of Routine Post-Treatment Surveillance
in Prostate Cancer Survivors**

National Clinical Trial (NCT) Identification Number: NCT02957357

Principal Investigator: [name]

20 Dec 2016

Study Protocol and Statistical Analysis Plan

Specific Aim 1: Compare patient-centered outcomes (including survival, procedures/tests, treatments) in prostate cancer survivors followed with alternative surveillance frequencies.

Hypothesis: More frequent surveillance increases the receipt of additional procedures and tests in all groups of patients, but improves survival only in patients with high-risk prostate cancer.

Synopsis: We will analyze data from the National Cancer Data Base (NCDB), which includes real-world prostate cancer treatment, surveillance and outcomes data on ~70% of US patients. We will compare the effectiveness of the three most common surveillance frequencies (PSA testing every 3 months vs. 6 months vs. 12 months) stratified by risk of recurrence and initial treatment (surgery or radiation).

Introduction: The primary goal for PSA surveillance after prostate cancer treatment is to detect recurrent cancer, thus allowing provision of additional treatments which can improve survival.^{1,2} Intuitively, patients who are most likely to recur after initial treatment (“high risk” cancer) may require more frequent surveillance, while those least likely to recur (“low risk”) may require less frequent surveillance. Further, patients treated by surgery vs. radiation may require different surveillance frequencies because the definitions of recurrence differs by treatment, and false positives from surveillance PSA are much more common after radiation.^{3,4} These considerations underlie the rationale to examine outcomes separately in 6 individual groups based on *standard definitions* of recurrence risk⁵ and initial treatment:

- Low-risk prostate cancer (defined by clinical stage \leq T2a, PSA <10, and Gleason score \leq 6): Recurrence risk is <10%.⁶ Two cohorts will be examined separately, 1) those treated with **initial prostatectomy**, and 2) those treated with **initial radiation** (including external radiation and/or brachytherapy).
- Intermediate-risk prostate cancer (defined by clinical stage T2b-c, and/or PSA 10-20, and/or Gleason 7): Recurrence risk is ~30%.⁷ Two cohorts will be examined separately, 3) those treated with **initial prostatectomy**, and 4) those treated with **initial radiation**.

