- High-risk prostate cancer (defined by clinical stage \geq T3, PSA >20, or Gleason 8-10): most aggressive type of prostate cancer. Recurrence risk is ~50%.⁷ Two cohorts will be examined separately, 5) those treated with **initial prostatectomy**, and 6) those treated with **initial radiation**.

[figure not shown]
The objective of this aim is to quantify the potential benefits (survival) and harms (procedures/tests, treatments) of different PSA surveillance frequencies in the 6 patient groups, which are currently unknown. It is intuitive that more frequent surveillance will lead to more findings of elevated PSA, thus leading to more downstream procedures and tests, and treatments; with unclear survival benefit. The *rationale* for this aim is that successful completion of the proposed research will contribute novel, currently unavailable, data to inform patient decision-making.

Comparators [RQ-5]: We selected our comparators of surveillance frequency based on published recommendations and by engaging diverse stakeholders (including clinicians who specialize in prostate cancer care). The three most common surveillance frequencies in clinical

practice are every 3, 6, or 12 months. In each of the 6 patient groups, patient outcomes of every 3 vs. 6 vs. 12 month surveillance will be directly compared. We will define our surveillance groups based on the number of PSA tests patients receive during the first year following completion of prostatectomy or radiation therapy (Figure) – using an “intention to treat” approach – and analyze patient outcomes from Years 2-10. Operationally, we will compare the outcomes of patients who have 1 vs. 2-3 vs. ≥ 4 PSA tests within the first year. We selected this timeframe as we believe that these patterns would be reflective of the physician’s intended surveillance schedule as opposed to later years which may be more reflective of patient adherence to surveillance recommendations.

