The analysis is stratified by two important factors, risk of recurrence (low, intermediate, high) and type of initial treatment (surgery, radiation); thus, 6 separate analyses will be performed. All outcomes will be defined from years 2-10 from end of prostatectomy or radiation treatment (Figure 1). We will use two modeling strategies to evaluate our outcomes of interest: 1) modified Poisson/binary regression^{19,20} with sandwich standard errors to estimate risks of the events of interest during a set follow-up period; and 2) Cox Proportional Hazards regression [CI-3]. Using the modified Poisson/binary regression models, we will estimate the risk of experiencing the outcome of interest (death, recurrence, use of procedures and tests, treatment for recurrence) during a defined interval beginning in the second year following treatment. Additionally, we will estimate overall survival using adjusted Cox Proportional Hazards regression models. We will evaluate the proportional hazards assumption by generating Kaplan-Meier survival curves and through testing interactions between relevant covariates and time in the Cox model. Covariates that violate the proportional hazards assumption will be used as stratification variables as appropriate. In sensitivity analyses, we will generate a propensity score (where the patient, provider and hospital characteristics measured at the time of prostatectomy or radiation completion are included in the propensity score) and create a matched cohort of patients to evaluate using Kaplan-Meier survival models [described in detail in C3]. For secondary outcomes, time to recurrence will be modeled for each surveillance frequency using a competing risk analysis as described by Fine and Gray.²¹ Similar methods will be used to calculate the cumulative incidence of procedures and tests and treatment for recurrence.

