Several outside/environmental factors can affect a patient's surveillance frequency. In our preliminary analysis using the US population-based Surveillance, Epidemiology and End Results (SEER)-Medicare dataset, we found race, marital status, and regional socioeconomic determinants (high school graduation rate) to be associated with different PSA surveillance frequencies. The NCDB captures a comprehensive list of covariates (see above). We will examine if surveillance frequency is associated with each individual factor and account for these factors using modeling as above. Finally, we recognize that there may still be important unmeasured confounders in our study; therefore, we plan to use sensitivity analyses to estimate the impact of a hypothetical unmeasured/unobserved confounder, using similar methodology used in a prior study by the co-I ([name]).²² This analysis will allow us to determine the extent of confounding that would substantively change our study findings.

A conceptual diagram (directed acyclic graph) demonstrating the relationship between measured covariates and our selected study outcomes for Aim 1 is provided in Figure 2 below.

Figure 2. Directed Acyclic Graph for the Hypothesized Relationship between Selected Study Variables and Outcomes for Aim 1

Footnote: Analyses will be stratified by the type of initial treatment (surgery, radiation) and recurrence risk (low, intermediate, high) and the hypothesized relationships may vary somewhat by each clinical scenario. Relationship between variables identified as pertaining to Aim 2 are noted in Figure 3.

Statistical power: There are >1,400 CoC-accredited hospitals. With 10 patients sampled at each hospital, we expect 14,000 patients will be available for analysis. We will intentionally sample approximately the same number of patients in each of the 6 cohorts (risk group x primary treatment), providing 2,333 patients in each cohort. Within each cohort, patients receiving different surveillance frequencies will be compared. Based on preliminary analysis of SEER-Medicare data, the national patterns of PSA surveillance in the first year are: (Table 2)

Number of PSAs	Low Risk	Intermediate Risk	High Risk
1	20%	18%	17%
2-3	61%	59%	53%
4	19%	23%	30%

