Power calculations used a range of 10-year overall survival rates from 70-80%, $\alpha=.05$, and two-sided test. Using distributions in Table 2, there is >80% power to detect a 5% survival difference among groups of different surveillance frequencies. Our stakeholders have indicated this level of survival difference to be meaningful.

Potential problems and alternative strategies:

Although the analysis will stratify by prostate cancer risk status, it is possible that within each

risk strata, patients with clinical and pathological features that are associated with a worse prognosis may be followed more frequently than patients with a better prognosis. One way we have proposed to address this issue is with instrumental variable analysis (Page 11). We will test two commonly-used, potential instrumental variables: region and the provider's most commonly used surveillance regimen (commonly called “provider preference”). Another way to address this in our primary analysis is to account for risk variables (clinical and pathological features) within each risk strata. We will plan to incorporate this in the primary analysis as control variables within the outcome models or within the propensity score model, as appropriate to the research question.

Our definition of comparison groups is based on published recommendations and stakeholder guidance. However, schedules for surveillance PSA tests in this observational cohort may not precisely match the anticipated 3, 6, and 12 month intervals. Multiple classification schemes will be assessed for characterizing the surveillance intervals, as described on page 2. The analysis will be repeated using alternative classification schemes, and sensitivity analyses will be used to determine if there are meaningful differences in the results based on classification of surveillance intervals, and to optimize our classification of surveillance frequency [IR-5].

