Patients treated within a site may be more similar with regard to surveillance frequency than patients treated within other sites. Given this, we will evaluate the need for clustering patients within sites by estimating the variance in surveillance frequency and outcomes within versus between sites. If clustering is indicated we will incorporate a site level term into our regression models as 1) a grouping variable; 2) as a fixed effect within the regression model (to control for time-invariant omitted variables and methodological artifacts of temporal correlation), and 3) as a random effect (to control for unobserved heterogeneity which may be constant over time and correlated with independent variables). These analyses will be in addition to the analytic techniques previously proposed (propensity score and instrumental variables methods), which provide alternative approaches to examining for these issues, and are discussed in C3. If the variation between clusters is small, we will present regression results without clustering (focused on patient-level analyses) for our primary analytic strategy.

We will assess the prevalence of patients receiving treatment before meeting official definition of recurrence, and whether this prevalence is similar or different in the comparison groups. In our primary analysis, we will assess outcomes (procedures, treatments) regardless of whether patients received treatments before meeting official definition of recurrence – because this is likely the result of patient/physician anxiety caused by frequent PSA surveillance testing. However, in sensitivity analysis, we will exclude patients who received treatment before meeting official definition of recurrence.

C2. Specific Aim 2: Compare patient-reported outcomes in prostate cancer survivors followed with alternative surveillance frequencies.

Hypothesis: More frequent surveillance is associated with more patient-reported anxiety and worse health-related quality of life.

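### Aim 1 hypothesises a survival benefit only in high-risk patients, but no planned analysis tests the *only* part of that claim

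*Combined protocol and SAP*

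**What the plan says.** All references are to the combined protocol and SAP, Specific Aim 1 unless stated.

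- Hypothesis: more frequent surveillance raises the use of procedures and tests in all groups but "improves survival only in patients with high-risk prostate cancer".
- Comparators: "In each of the 6 patient groups, patient outcomes of every 3 vs. 6 vs. 12 month surveillance will be directly compared".
- Data Analysis: the analysis is stratified by risk and initial treatment; "thus, 6 separate analyses will be performed".
- Statistical power: "Within each cohort, patients receiving different surveillance frequencies will be compared". A 5% survival difference is the difference to detect, and "Our stakeholders have indicated this level of survival difference to be meaningful".
- The only interactions named are for the proportional hazards check: "testing interactions between relevant covariates and time in the Cox model".
- C3 (Avoidance of bias) mentions effect heterogeneity once, as a reason to apply the propensity score by both weighting and matching. Risk groups are not mentioned there.

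Overall survival is the primary outcome (Outcomes). The stated objective is to quantify benefits and harms in the six groups.

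**The concern.** *Only in high risk* makes three statements: there is a benefit in high risk; it is larger there than in low and intermediate risk; and there is no benefit that matters in the other two. The cohort models address the first. The second needs a contrast between risk groups, and the third needs a margin to read the low- and intermediate-risk intervals against. The plan has neither.

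A significant result in one cohort and a non-significant one in another does not show that the effects differ, and non-significance does not show absence of benefit. The results are meant to inform patients' decisions. A conclusion that frequent testing lengthens survival only in high-risk men tells the others that they gain nothing. Without a stated criterion, that conclusion would have to be judged after the results are seen.

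**Working it through.** **Inputs.** From Statistical power: 14,000 / 6 = 2,333 per cohort; 14,000 / 3 = 4,667 per risk group when treatments are pooled; two-sided α = 0.05; 10-year survival 70–80%; 5% difference (read here as percentage points). Table 2 shares for 1 / 2–3 / ≥4 tests: low 20/61/19%, intermediate 18/59/23%, high 17/53/30%.

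**Assumptions.** Survival 70 vs 75% or 75 vs 80%; unadjusted; 10-year status fully observed; independent cohorts; no site clustering; each frequency pair taken as a separate scenario. Survival by risk group is not given, so ranges are shown.

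**1. The plan's own figure.** It states more than 80% power for 5 points. I used a two-proportion test: power = Φ[(0.05 − 1.96·s0)/s1], with s0 the pooled and s1 the unpooled standard error. Example, high risk, 2–3 vs ≥4, 70 vs 75%: n = 1,236 and 700, s0 = 0.0213, s1 = 0.0209, power 65%.

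| Pair | Survival | Low | Interm. | High |
|---|---|---|---|---|
| 1 vs 2–3 | 70/75 | 0.57 | 0.53 | 0.50 |
| | 75/80 | 0.63 | 0.59 | 0.56 |
| 2–3 vs ≥4 | 70/75 | 0.53 | 0.59 | 0.65 |
| | 75/80 | 0.58 | 0.64 | 0.71 |
| 1 vs ≥4 | 70/75 | 0.39 | 0.41 | 0.44 |
| | 75/80 | 0.44 | 0.46 | 0.49 |

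The 80% is not reproduced within a cohort (39–71%). That is a separate matter; the table is used here only as input.

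**2. Apparent *only* when all groups benefit equally.** P(high significant, low and intermediate not) = power_high × (1 − power_low) × (1 − power_int).
- 1 vs ≥4, 70/75: 0.436 × 0.608 × 0.593 = 0.157.
- 1 vs 2–3, 75/80: 0.561 × 0.375 × 0.411 = 0.086.
- Over all six scenarios: about 9–16% within one treatment.

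**3. Can low and intermediate risk exclude 5 points?** Half-width = 1.96·√[p(1−p)(1/n1 + 1/n2)].
- 1 vs ≥4: low risk at 70% gives 1.96·√[0.21(1/467 + 1/443)] = 5.96 points. The range over both risk groups and 70–80% is 5.1–6.0, so even an estimate of zero would not exclude 5 points.
- Other pairs: 4.0–5.0 points.
- With a true effect of zero, one cohort's interval excludes 5 points in 38–69% of cases, and both do in 15–44%. Pooled over treatment: 64–94% and 42–84%.

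**4. Power of the contrast.** Truth: 5 points in high risk, 0 elsewhere. Power = Φ[0.05/√(v_high + v_other) − 1.96], where v is the variance of a cohort's risk difference. Example, 2–3 vs ≥4, high minus intermediate, 70/75 with the null group at 70%: v_high = 0.000438, v_int = 0.000544, so Φ(0.05/0.0313 − 1.96) = 0.36.

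| Pair | One treatment | Pooled |
|---|---|---|
| 1 vs 2–3 | 28–34% | 49–59% |
| 2–3 vs ≥4 | 34–43% | 58–71% |
| 1 vs ≥4 | 23–27% | 40–48% |

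The plan itself raises clustering ("Patients treated within a site may be more similar with regard to surveillance frequency than patients treated within other sites"). An assumed design effect of 1.2 lowers each contrast to 20–37% within one treatment and 34–63% pooled.

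**5. The three-part rule, by simulation (400,000 draws).**
- Truth 5 / 0 / 0: met in about 5–20% of cases within one treatment and 18–52% pooled.
- Same 5- or 2.5-point benefit in all groups: met in under 0.5%.
- Truth 0 in high risk and −5 points elsewhere, 2–3 vs ≥4: a rule without the requirement that the high-risk effect exceed 0 is met in 17–19% (one treatment) and 40–44% (pooled). With that requirement it is met in about 2%. The requirement costs about half a point of power or less in the 5 / 0 / 0 case.

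**The case against.** The strongest reply is that Aim 1 sets out to quantify effects in six groups, gives reasons for analysing them separately, and does that. This stands: the six analyses should stay, and nothing here makes their estimates invalid. It does not remove the word *only* from the hypothesis.

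A reader might infer more than the documents support, in two ways:

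- *The plan will infer a high-risk-only benefit from one significant and two non-significant cohorts.* It does not say so. It states no criterion at all, so the 9–16% describes a possible reading, not a planned one.
- *The Aim 1 hypothesis has no test.* Too broad. The cohort models in Data Analysis address the increase in procedures and tests and the survival benefit in high risk. Only the *only* component is untested.

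It can also be said that the contrast is underpowered. That is true. It is a reason for caution in claiming *only*; it does not justify leaving the criterion unstated.

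Finally, the 5-point difference is tied to 10-year survival, while Data Analysis gives 8–10 years of follow-up per patient. The margin cannot simply be carried over to an earlier time, and the fix has to deal with this.

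**Conclusion.** The concern holds in a limited form. Run exactly as written, the six analyses cannot support *only*: there is no between-risk-group contrast, and the 5-point difference serves only as the effect to detect, never as a margin to exclude. This rests on the text and depends on none of the figures above. The figures show that the gap matters: about 9–16% of cases per comparison within one treatment would give an apparent high-risk-only pattern under a shared 5-point benefit, on the assumptions listed. Cohort-specific estimates and the stated objective are unaffected. The change should be made, and it is cheap.

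**What to change.** Keep the six analyses and do one of the following.

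1. **Reword.** Remove *only* from the hypothesis and report cohort-specific effects with 95% CIs. This costs nothing.

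2. **Add a test of *only* to the SAP.** Pre-specify the high-minus-low and high-minus-intermediate differences in the survival effect with 95% CIs, within each treatment and pooled over treatment. Do this for one frequency comparison and one fixed time point that the follow-up supports, and state how the 5-point margin, set for 10-year survival, applies at that time. Conclude a benefit only in high risk only if all three hold:
   - the 95% CI of the high-risk effect lies above 0;
   - the 95% CIs of both between-risk-group differences lie above 0;
   - the 95% CIs of the low- and intermediate-risk effects exclude a 5-point benefit.

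   Otherwise report cohort-specific estimates without *only*. Say that the rule supports no benefit of 5 points or more elsewhere, not no benefit at all. State whether the rule applies within treatment (matching the six-cohort design) or pooled (the hypothesis names risk alone). Show treatment-specific contrasts beside any pooled one, because the Introduction gives reasons for separating treatments.

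The choice of frequency pair, or of a trend across the three levels, is for the investigators, provided it is fixed in advance.

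Cost of option 2: a few lines of text and no new data. The contrasts are differences between estimates already planned. Absolute differences can come from the planned risk model, which covers events "during a defined interval beginning in the second year following treatment", with standardisation. The low chance of meeting the rule even when *only* is true should be stated in the plan.

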In sensitivity analysis, we will vary this timeframe to define surveillance frequency based on the timing of the first PSA test following completion of prostatectomy or radiation therapy (first PSA within 3 months vs. >3 but within 6 months vs. >6 months); or define comparison groups empirically (most frequent 1/3 of patients vs. middle vs. least frequent 1/3 of patients) – to assess if our findings are robust to these varying exposure groupings [IR-5]. We will also explore using Years 1-2 to define surveillance frequency, and examining patient outcomes from Years 3-10.

Figure 1. Sample Identification and Definition of Timeframes for Measurement

Data Source [IR-1][DR-2][PC-2]: The National Cancer Data Base (NCDB) is a joint program between the Commission on Cancer (CoC) of the American College of Surgeons and the American Cancer Society.⁸ NCDB, started in 1989, is a nationwide cancer outcomes database that includes $>1,400$ CoC-accredited cancer programs and $\sim 70\%$ of all newly diagnosed cancer cases in the US – making its data broadly generalizable and ideal for CER.⁸⁻¹⁰ Systematic, longitudinal follow-up data are updated annually, with multiple data-quality assurance steps taken. **The high quality and representative NCDB data are used for the annual US “cancer statistics” report.**^{11,12} Thus, our results using the NCDB optimizes external validity and generalizability. Data elements are recorded by certified cancer registrars using nationally standardized data item and coding definitions specified by the Facility Oncology Registry Data Standards. Detailed information about data elements collected by the NCDB, standardized data collection protocol, and quality control methods used to assess reported case information is available at: www.facs.org/cancer/ncdb/datasubmission.html.

NCDB Special Study mechanism for primary data collection will be used to obtain the detailed level of information required for this study on data elements which do not currently exist in the NCDB registry – including PSA frequency – and to fill in missing data [MD-1].¹³⁻¹⁵ This will be done using chart abstraction by each of the CoC-accredited centers. For this Aim, the NCDB will randomly select 10 prostate cancer patients diagnosed in 2005-07 from each CoC-

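### The last group of the first-PSA-timing sensitivity analysis has no upper limit, so men first tested after month 12 enter it with guaranteed survival inside the outcome window and have no counterpart in the primary groups

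*Combined protocol and SAP*

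**What the plan says.** All of this is in Specific Aim 1 of the combined protocol and SAP.

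- **Primary exposure (Comparators).** Groups are formed "based on the number of PSA tests patients receive during the first year following completion of prostatectomy or radiation therapy". In practice, "we will compare the outcomes of patients who have 1 vs. 2-3 vs. ≥ 4 PSA tests within the first year". No group is given for zero tests, and no readable text says such men are excluded.
- **First-PSA sensitivity analysis (Comparators).** "In sensitivity analysis, we will vary this timeframe to define surveillance frequency based on the timing of the first PSA test", with the groups "first PSA within 3 months vs. >3 but within 6 months vs. >6 months". The last group is not bounded above. A second alternative splits men empirically into thirds by testing frequency.
- **Outcome window (Data Analysis).** "All outcomes will be defined from years 2-10 from end of prostatectomy or radiation treatment".
- **A further alternative (Comparators).** "We will also explore using Years 1-2 to define surveillance frequency, and examining patient outcomes from Years 3-10". Here the start of outcome follow-up moves with the exposure window.
- **Numbers (Statistical power).** With 10 men from each of more than 1,400 hospitals, "we expect 14,000 patients will be available for analysis", or 2,333 in each of six cohorts. Table 2 gives the Year-1 split over 1, 2-3 and 4 tests, with no row for zero.

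**The concern.** A group should be fixed by information available when outcome follow-up starts. The primary definition meets this: the Year-1 count is complete at month 12. The first-PSA definition does not. For a man first tested after month 12, membership of the last group is settled inside the outcome window and requires that he survived to the test. That is immortal time.

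Two things are at stake.

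- **Direction.** The guaranteed survival goes to the least-surveilled group. It works against the hypothesised survival benefit of frequent testing in high-risk men, so it could make a true primary result look less robust.
- **Interpretation.** The check is meant to show whether findings depend on how exposure is grouped. If it also admits men who are in no primary group, a discrepancy could come from the grouping, the added men or the guaranteed survival, and the analysis could not tell these apart.

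**Working it through.** The plan states no figure for this point, so there is none to reproduce. The check is to assign cases by the written rules and then size the effect.

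**Step 1. Assign cases.**

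| Testing pattern | Primary group | First-PSA group | When the group is known |
|---|---|---|---|
| First PSA at month 8, one test in Year 1 | 1 test | over 6 months | before outcomes start |
| First PSA at month 14, none in Year 1 | none | over 6 months | 2 months into the outcome window |
| First PSA at month 20, none in Year 1 | none | over 6 months | 8 months into the outcome window |
| Dies untested at month 16 | none | none | never assigned |
| Alive, never tested | none | none (no first PSA) | never assigned |

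The problem lies in rows two and three, set against row four.

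**Step 2. Death risk avoided by one late-tested man.** Inputs: 10-year overall survival S of 70% to 80% (Statistical power) and, as a simplification, a constant hazard.

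- h = -ln(S)/10: 0.0357 per year at S = 0.70; 0.0223 at S = 0.80.
- Risk removed by m guaranteed months after month 12: 1 - exp(-h*m/12).
- First PSA at month 18 (m = 6): 1.1 points (S = 0.80) to 1.8 points (S = 0.70).
- First PSA at month 24 (m = 12): 2.2 to 3.5 points.

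**Step 3. Effect on the group.** Multiply by the share of the group first tested that late. The documents do not give this share, so it is an assumption and a range is shown.

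| Assumed share | First PSA at month 18 | First PSA at month 24 |
|---|---|---|
| 10% | 0.1-0.2 points | 0.2-0.4 points |
| 25% | 0.3-0.4 points | 0.6-0.9 points |
| 50% | 0.6-0.9 points | 1.1-1.8 points |

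These are gaps in survival at the end of the guaranteed period. Carried to year 10 under the same hazard, the gap per man is exp(-9h)*(exp(h*m/12) - 1). With a 25% share that is 0.2-0.3 points (month 18) and 0.5-0.7 points (month 24). The comparison is the 5-point difference used for power.

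**Step 4. Is a 25% share conceivable?** Suppose, crudely, that the last group in a low-risk cohort were made up of all zero-test men and all one-test men (20% of tested men, Table 2), and no one else. If a fraction x of the cohort has no Year-1 test, the zero-test share is x/(x + 0.20*(1 - x)). For x = 2%, 5%, 10% and 20% (assumed) this gives 9%, 21%, 36% and 56%. So 25% is possible, but nothing in the documents establishes it.

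**Step 5. Planning numbers.** Table 2 columns sum to 100%: 20+61+19, 18+59+23, 17+53+30. Also 14,000/6 = 2,333. Every sampled man is therefore counted as analysable and spread over groups that begin at one test.

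**The case against.** - **Figure 1 may settle it.** It defines sample identification and timeframes, and it is not shown. If it requires at least one PSA in Year 1, the last group already means over 6 to 12 months and the point disappears. This cannot be excluded. No readable text states such a rule, and the sensitivity analysis is introduced as varying the timeframe, so the 12-month limit cannot be presumed.
- **Leaving zero-test men out of the primary analysis fits the question.** It compares three schedules, each implying at least one test a year. This stands: the primary grouping needs no change, only a stated rule.
- **The plan already separates windows and promises several schemes.** It does so for the Years 1-2 scheme, which shows that the principle is accepted, but not for first-PSA timing. The missing-data section (C3) does not help, because zero tests is an observed value.
- **The bias is small and easily filtered, since PSA dates are abstracted.** Both are true. That limits the weight of the point and makes the remedy nearly free.

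A reader might also infer stronger things that the documents do not support:

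- *That all men without a Year-1 PSA fall in the last group.* Never-tested men have no first PSA and so no group.
- *That the tertile analysis has the same bias.* A Year-1 count of zero is known at month 12, so it creates no immortal time. What is open is only whether those men are included.
- *That 2,333 analysable men per cohort cannot be reached.* The plan counts more than 1,400 hospitals, any loss percentage would be assumed, and Table 2 may describe tested men only.

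**Conclusion.** The point holds on the text as written. The rule as stated gives guaranteed survival time to men first tested after month 12, and it brings into the check men who have no primary group. The distortion is confined to one sensitivity analysis; the primary estimate is not affected. Its size is modest: the 0.3 to 0.9 points rest on a 25% share, first tests at months 18 to 24, a constant hazard and the plan's 70-80% survival range. The change of population is present whatever the share. The conclusion is conditional on Figure 1 not already restricting the sample. On numbers, the supportable statement is only that the plan does not distinguish men sampled from men analysable; a shortfall is not shown.

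**What to change.** Unless Figure 1 already does this, in which case one confirming sentence is enough:

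1. Cap the last first-PSA group at over 6 to 12 months, so that exposure is complete before outcomes begin.
2. Define one analysis set for the primary, first-PSA and Year-1 tertile analyses: alive at the start of Year 2, with at least one PSA in Year 1. State how many men are left out for each reason.
3. Keep the Years 1-2 scheme with outcomes from Year 3 as it is.
4. Under Statistical power, describe 14,000 (2,333 per cohort) as the number sampled, and report the analysable number once men with no Year-1 PSA or a death in Year 1 are removed.

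The cost is SAP wording and a filter on data already being collected: PSA dates through the special study, vital status and treatment dates from the registry. The downside is that the analysable number may be slightly smaller than the one now stated.
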